2. To evaluate the effect of NSS on clinical and biochemical changes among patients.
3. To evaluate the effect of NSS on the biochemical status associated with overall mortality.

Study hypotheses

The null hypothesis: The nutritional support system will not reduce mortality or increase survival in patients with COVID-19 in stage III and comorbidities compared to conventional nutritional therapy.

Research hypothesis: The nutritional support system will reduce mortality and increase survival in patients with COVID-19 in stage III and comorbidities compared to conventional nutritional treatment.

Section 3: Trial Methods

9. Trial design - description of trial design

Item 9: Brief description of trial design including type of trial

Randomized, blinded, controlled clinical trial. Selected patients will be randomized into two groups: 1) Control Group (CG) will receive the hospital diet and 2) Intervention Group (IG) will receive the hospital diet and the NSS. Treatment allocation will have a 1:1 ratio.

10. Randomization

Randomization will be performed using a raffle; eighty numbers are to be placed (from 1 to 80). Subsequently, each number will be randomly selected from the raffle and sequentially assigned to one of the two groups, until reaching 40 numbers per group. Each number represents the moment the patient enrolls. In this way, once the recruitment starts, the first patient will be assigned number one; the second will be number two, and so on.

11. Sample size

Item 11: Full details of the same size calculation or alternatively reference to sample size calculation in protocol (instead of replication in SAP).

The sample size will be calculated using the formula: $n = \frac{z^2 p q}{e^2}$, where: 95% confidence level ($z = 1.96$), $p = 0.975$, $q = 0.025$, with a margin of error of 5% ($e = 0.05$), obtaining 38 patients per group for the sample.

12. Framework

Item 12: Superiority, equivalence or non-inferiority trial hypothesis testing framework, and wick comparisons will be presented on this basis.

The effect of NSS in increasing survival and reducing mortality in patients with COVID-19 will be demonstrated by the significant superiority of IG over CG.

13. Statistical Interim analyses and stopping guidance

Item 13a: Information on interim analyses specifying what interim analyses will be carried out and listing of time points:

No interim analyses are planned in the study.

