Item 13b: Any planned adjustment of the significance level due to interim analysis:

No adjustment of the significant level due to interim analysis are planned.

13c. Details of guidelines for stopping a trial early:

The following points are considered in planning the early stopping of the study:

1. That the intervention causes serious adverse effects in patients generating insecurity in its application.
2. That the investigators detect improbable, ineffective, or extreme differences between the CG and the IG.

3. New information emerges that raises serious safety issues or convincingly answers to the main question.

14. Timing of final analysis

Item 14: Timing of final analysis e.g all outcome analyzed collectively or timing stratified by planned length of follow-up

The follow-up will start in September 2020 until the established sample is met.

The last day of the study for each patient is going to be 40 days after hospital discharge.

Statistical analysis of clinical and biochemical variables will be performed on baseline, day three, hospital discharge and day 40. Analysis of overall survival and mortality will be performed from baseline to day 40 or patient death. Progression of patients to Mechanical Ventilation Assistance (MVA) will be performed from baseline until the last patient is intubated, mortality in patients with MVA will be performed from intubation to day 40 or death.

15. Timing of outcome assessments

Item 15: Time points at which the outcomes are measured

Survival and Mortality

- Overall survival and mortality: performed from baseline to day 40 or patient death.
- Progression of patients to Mechanical Ventilation Assistance (MVA): performed from baseline until the last patient is intubated.
- Mortality in patients with MVA: performed from intubation to day 40 or death.

Clinical and biochemical variables

- Delivered oxygen flow and maintenance of SpO₂ > 90%: will be analyzed at baseline and day three.
- qSOFA scale: will be analyzed at baseline compared with day three.

- Gastrointestinal function (average of gastrointestinal movements, abdominal distension, and Bristol scale): will be analyzed at baseline compared with day three.
- Laboratory parameters: will be analyzed at baseline, day three and hospital discharge.
- PHQ-9: will be analyzed at baseline and hospital discharge.

Follow-up at day 40

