- SpO2 without supplemental oxygen, use of home oxygen upon hospital discharge, days of supplemental oxygen use, post-covid syndrome, decrease in body weight: all will be analyzed from hospital discharge until day 40.

Section 4: Statistical Principles

16. Confidence intervals and p-values

Item 16: Level of statistical significance

P values ≤ 0.05 will be considered indicative of statistical significance in all cases. P values will be one-sided.

Item 17: Description of any planned adjustment for multiplicity, and if so, including how the type I error is to be controlled

This study will not analyze data that required multiplicity tests. To avoid type 1 error, an alpha value of 5% will be used (considering $p < 0.05$ significant), aberrant data will be eliminated, validated tests applicable to the study variables will be defined and established, specific inclusion criteria will be implemented for homogenization of the sample to avoid bias variables, and a specific sample size calculation will be performed.

Item 18: Confidence intervals (CI) to be reported

All the confidence intervals presented will be 95%.

19. Adherence and Protocol Deviations

Item 19a: Definition of adherence to the intervention and how this is assessed including extent of exposure.

The intervention will consist of: 1) 2 envelopes of NSS taken in a period of less than 15 minutes (without the presence of vomiting) after morning and afternoon meals during the first 21 days or until hospital discharge, 2) 1 capsule of *Saccharomyces Boulardii* before the NSS and 1 capsule with the second envelope for 6 days or until hospital discharge, 3) intramuscular B complex; 1 ampoule after meals for 5 days or at hospital discharge.

Adherence to treatment will be established as taking more than 95% of the NSS and not fasting for 2 consecutive days.

Item 19b: Description of how adherence to the intervention will be presented

The intervention will be applied by the research team, who will be responsible for the application and collection of data, which will be reported in daily formats in the morning and afternoon shifts.

The clinical investigators are going to prepare each supplement, administer, and witness each intake of the NSS, registering the time as well as any immediate side effects such as vomiting, bloating, and abdominal pain.

Item 19c: Definition of protocol deviation for the trial:

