The following will be considered major violations of the predefined protocol that could affect the primary outcome:

- Failure to meet the inclusion criteria.
- Failure to sign the informed consent letter.
- Failure to follow protocol procedures that specifically relate to the primary endpoints of safety or efficacy of the study.

Item 19d: Description of which protocol deviations will be summarized (may include details of whether deviation is major or minor and impact on analysis populations and approach to summarizing protocol deviations e.g. number and type of protocol deviation, per group).

Deviations from the protocol will be classified before concluding the study. The number and percentage of patients with major and minor deviations from the protocol will be summarized by study group with details of the type of deviation provided. The patients included in the analysis data set will be used as the denominator to calculate the percentages.

20. Analysis populations

Item 20: Definition of analysis populations e.g intention-to-treat (ITT), per-protocol, complete case, safety.

Patients with COVID-19 stage III, both sexes between 30 and 75 years with comorbidities (DM2, SAH, BMI 25-40). We will select 80 patients divided into two groups: CG (hospital diet), and IG (hospital diet + NSS).

Both groups will be analyzed for 1) survival and mortality, 2) clinical and biochemical variables, and 3) follow-up 40 days after discharge.

Section 5: Trial Population

21. Screening Data

Item 21: Reporting of screening data (if collected) to described representativeness of trial sample

The screening data report and screening data will be included in the manuscript in the following sections:

1. Consort figure based on CONSORT 2010 guidelines.
2. Table showing demographic analysis of the patients.

3. Table showing baseline results.
4. Summary of screening data described in the first part of the results section.

22. Eligibility

Item 22: Summary of eligibility criteria

The inclusion and exclusion criteria will be indicated in the methods section. The selected and non-selected patients will be included in the CONSORT diagram, where the causes of ineligibility will be indicated.

23. Recruitment

Item 23: Information to be included in the CONSORT flow diagram

A CONSORT flow diagram will be used that will include the following study and patient information:

- Assessed for eligibility at screening.
- Eligible at screening.

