The probable adverse effects that could occur are intolerance to formula components, allergic reactions, constipation, headache, rash, and gastrointestinal disturbances. If constipation occurs, the amount of water in patients will be adjusted.

31. Statistical Software

Item 31: Details of statistical packages to be used to carry out analyses (optional)

The analysis will be carried out using Graphpad Prism version 6 software and SPSS Statistics 25 version.

32. References

Item 32a: References to be provided for non-standard statistical methods.

- LCTC - Declaración de SAP [Internet]. Org.uk. Available at: <https://www.lctc.org.uk/SAP-Statement>

Item 32b: Reference to Data Management Plan

- LCTC - Declaración de SAP [Internet]. Org.uk. Available at: <https://www.lctc.org.uk/SAP-Statement>

Item 32c: Reference to the Trial Master File and Statistical Master File

- LCTC - Declaración de SAP [Internet]. Org.uk. Available at: <https://www.lctc.org.uk/SAP-Statement>

Item 32d: Reference to other Standard Operating procedures or documents.

- LCTC - Declaración de SAP [Internet]. Org.uk. Available at: <https://www.lctc.org.uk/SAP-Statement>

CONSORT
TRANSPARENT REPORTING OF TRIALS

[figure not shown]

Figure 1. Consort, transparent reporting of trials.

Table 1-A. Clinical characteristics and demographic analysis.

Characteristics	CG	IG	P- value
	Mean (SD / %) n=40	Mean (SD / %) n=40	
Median age – years.	53.9 ± 10.3	51.5 ± 11.4	0.351
Female gender – no. (%)	13 (32.5%)	15 (37.5%)	0.407
Male gender – no. (%)	27 (67.5%)	25 (62.5%)	0.407

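### Side effects as such are registered only around NSS intake, so controls have no equivalent adverse-event record, and no harms summary by arm is planned

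*SAP*

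**What the plan says.** SAP Item 19b, an item on presenting adherence, has the clinical investigators prepare and give each supplement and "witness each intake of the NSS, registering the time as well as any immediate side effects such as vomiting, bloating, and abdominal pain". Only the intervention group (IG) takes the NSS. The control group (CG) receives the hospital diet and usual treatment (Items 9 and 23).

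Item 30 (Harms) names six probable effects: "intolerance to formula components, allergic reactions, constipation, headache, rash, and gastrointestinal disturbances". It adds one response to constipation. It does not say how or when these effects are collected, what counts as an event, or how the arms are compared.

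Item 13c point 1 gives as a ground for early stopping "That the intervention causes serious adverse effects in patients generating insecurity in its application". Point 2 refers to "improbable, ineffective, or extreme differences between the CG and the IG". Item 13a states "No interim analyses are planned in the study". Item 19c defines one type of major deviation by procedures tied to the "primary endpoints of safety or efficacy of the study", yet the objectives (Item 8), outcomes (Item 26a) and analysis table (Item 27) list no safety endpoint.

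Other data exist in both arms. Item 15 says "Gastrointestinal function (average of gastrointestinal movements, abdominal distension, and Bristol scale): will be analyzed at baseline compared with day three", and it schedules laboratory tests at baseline, day three and discharge. Items 26a and 27 make death and progression to intubation primary outcomes and compare gastrointestinal symptoms at day 40. The protocol's Procedure section adds daily vital signs, clinical evaluation and a bowel record, not limited to one arm. Item 23 foresees an undefined line for incidents in the CONSORT diagram.

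**The concern.** A harm count is interpretable only if both arms are asked the same questions, at the same times, against the same baseline. Here the trigger for recording is the treatment itself. Headache, vomiting, distension and altered bowel habit are also part of COVID-19 and its hospital care, so a count from treated patients alone mixes the disease with the product.

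Two features add to this. The investigators who give the NSS also register its effects, and no placebo is described although the trial is called blinded. In addition, Item 24a has patients with reactions leave the study. Their data are kept, but it is not stated whether their harm follow-up continues. The trial could then report a survival benefit without a sound comparison of tolerability, and the first stopping criterion, which turns on causation, would have no control experience to set beside it.

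**Working it through.** **1. The plan's own figures.** The sample-size formula (SAP Item 11) reproduces: 1.96² × 0.975 × 0.025 / 0.05² = 37.46, rounded up to 38. It contains no harm rate and no between-arm difference, so it gives no assurance about harms.

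Table 2-A confirms that some two-arm data exist. Its percentages give these counts, with one-sided Fisher tests:
- Day-3 distension: CG 16/31 (51.6%), IG 6/31 (19.4%); p = 0.008, as stated.
- Day-40 gastrointestinal symptoms: CG 4/24 (16.7%), IG 3/37 (8.1%); p = 0.266, as stated.

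**2. Explicit records after baseline, by term.**

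| Term | IG | CG |
|---|---|---|
| Formula intolerance | intake record | not applicable |
| Gastrointestinal disturbance | intake record; day 3; day 40 | day 3; day 40 |
| Vomiting, abdominal pain | intake record, if immediate | none explicit |
| Constipation | bowel record | bowel record |
| Allergic reaction | intake record, if immediate | none explicit |
| Rash | none explicit unless immediate | none explicit |
| Headache | none explicit | none explicit |

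Of the six Item 30 categories, three do not fit the intake record: constipation, headache and delayed rash. Delayed allergic reactions make it four on a strict reading. Constipation is partly covered in both arms by the bowel record.

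**3. Background frequency (SAP Table 1-A, 40 per arm).**
- Headache: IG 29/40 = 72.5%, CG 26/40 = 65%.
- Distension: 28/40 = 70% in each arm.
- Nausea and vomiting: IG 7/40 = 17.5%, CG 6/40 = 15%.

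If the CG baseline shares persisted and the NSS had no effect, 40 × 0.65 = 26 IG patients would have headache and 40 × 0.15 = 6 would have nausea or vomiting. A count from the IG alone has nothing to set against these numbers.

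**4. What equal recording could show at 40 v 40.** Fisher's exact test at 0.05, with 6/40 events in controls, needs at least 14/40 in the IG (15/40 two-sided). The IG rates below are assumptions.

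| True rates, CG v IG | Power, one-sided | Power, two-sided |
|---|---|---|
| 15% v 30% | 40% | 28% |
| 15% v 35% | 59% | 46% |
| 15% v 40% | 75% | 64% |

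Equal recording removes the ascertainment problem. It does not give a powerful test, so the harms table should be read as estimates.

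**The case against.** The strongest reply is that controls are far from unobserved. Death and intubation, the gravest possible harms, are compared between arms as primary outcomes. Liver and renal tests are repeated, vital signs and a clinical evaluation are recorded daily, and bowel function, distension and day-40 symptoms are compared. All of this stands. A reader might infer that controls have no harm data, and the documents do not support that. What controls lack is an adverse-event record. The shared items are outcomes at fixed times, and the day-40 gastrointestinal figures rest on 24 CG and 37 IG patients, with deaths excluded.

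Other stronger readings also fail:
- **Most listed harms escape the record.** The effects named in Item 19b are examples, and the 15 minutes in Item 19a limit how long intake may take; they are not an observation window. The count is three of six, or four on a strict reading.
- **Item 30 leaves out the injection and the capsule.** The reference to the formula qualifies intolerance only; the other terms are unrestricted.
- **The stopping guidance never mentions controls.** Point 2 of Item 13c does name both groups, though not for harms and with no threshold. Point 1 can also be judged case by case, so a between-arm table is not its only possible basis.
- **The zero-event limit shows the size of the problem.** The exact two-sided 95% upper limit for 0/40, 1 − 0.025^(1/40) = 8.8%, follows from the sample size alone. Two-arm recording would not change it.

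**Conclusion.** The point holds as a fault in ascertainment and reporting, and it should be corrected. Side effects as such are registered in one arm and around intake. Headache, rash and delayed reactions have no explicit capture after baseline in either arm, and vomiting and abdominal pain have none in controls. No by-arm harms summary is planned, Item 19c points to safety endpoints that are not listed, and criterion 1 of Item 13c has no stated definition of serious and no control reference. With baseline headache at 72.5% v 65% and distension at 70% in each arm, IG-only counts cannot be attributed to the NSS.

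This rests on three assumptions. First, the symptoms in Table 1-A were present near the first dose; the table does not say so. Second, no annex or daily form outside the available text already holds a two-arm symptom log. Third, the day-40 items do not itemise these terms: neither post-COVID syndrome nor gastrointestinal symptoms is defined, so some overlap is possible.

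**What to change.** - **Items 19b and 30, collection.** Complete the same dated symptom and adverse-event checklist in both arms, on the daily follow-up from randomisation to discharge and again at the day-40 contact. Cover all Item 30 terms, vomiting, abdominal pain, reactions to any study component, and serious events. Count an event only if it is new or worse than the recorded baseline. State whether harm follow-up continues for patients who leave the study because of reactions.
- **Item 30, reporting.** Tabulate patients with each event by randomised arm, with risk differences and 95% confidence intervals. Label the table descriptive, given 40 per arm and no described placebo.
- **Item 19c.** Reconcile its mention of safety endpoints with the outcome list.
- **Item 13c point 1.** State what is meant by serious, and that this table informs the criterion alongside case-level review. No clinical stopping threshold is proposed here.

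The Figure 2 legend describes 40-day follow-up as completed between September 2020 and April 2021. If collection is over, the minimum is a by-arm table from existing records and a plain statement that harms were not ascertained equally.

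The cost is a short extra daily form for controls and one table. Disease symptoms will be counted in both arms, and recording by staff who know the allocation would remain a limitation.
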